CLINICAL INVESTIGATION PLAN

CIP ID: CSE2017-01K

Establish implant accuracy with X-PSI Knee System

A multi-center, prospective, non-controlled post market study

**Revision 02
08.12.2017**

STUDY SPONSOR

**Zimmer GmbH
[name]
P.O. Box
[name]
Switzerland
[contact]**

1 Synopsis

Title:	Establish implant accuracy with X-PSI Knee System– A multi-center, prospective, non-controlled post market study
Sponsor: Manufacturer:	Zimmer GmbH Zimmer CAS
Objectives:	The main purpose of this study is to evaluate the accuracy of the new X-PSI Knee System. This will be achieved by analyzing early postoperative imaging data with regards to the mechanical alignment and compare them with preoperative planning imaging data (reviewed and approved by the surgeon).
Hypothesis:	The use of the new X-PSI Knee System achieves the same accuracy with respect to mechanical alignment as with conventional instrumentation.
Endpoints:	
Primary endpoint: Achievement of mechanical leg alignment in HKA frontal plane (± 3 degrees) with X-PSI Knee System is as accurate as with standard instrumentation at 4-6 weeks post operation. The X-PSI Knee System cohort will be compared with current literature (70% of cases within ± 3 degrees). No control group will be studied.
 
Secondary endpoint: Cost-effectiveness as assessed by OR set-up time, surgery time and post-processing time.

Indication/ Target Population:	Patients which are treated either with Persona, Vanguard or NexGen total knee system
Inclusion Criteria:	
• Patient is 18 years of age or older.• Patient can follow the X-PSI Knee System imaging protocol as part of standard of care procedures.• Patient gets TKA treatment which follows the criteria of the appropriate Instruction for Use.• Patient is willing and able to cooperate in the required post-operative standard of care.• Patient is willing and able to complete scheduled follow-up evaluations as described in the Informed Consent.• Patient has participated in the study-related Informed

	Consent process and has signed the Ethics Committee approved 'Informed Consent'.
Exclusion Criteria	
 • Patient is unwilling or unable to give consent or to comply with the follow-up program. • Patient meets exclusion criteria of the appropriate Instruction for Use • Patients who have any condition which would in the judgement of the Investigator place the patient at undue risk or interfere with the study. Any patient who is institutionalized, or is a known drug abuser, a known alcoholic or anyone who cannot understand what is required from them • Patient is known to be pregnant
Study Design:	Multi-centre, prospective, non-controlled
Clinical Phase:	Post market
Number of Subjects:	Data will be collected from 70 TKA cases implanted by use of the X-PSI Knee System in up to 5 study centers
Length of Study:	1.5 years (0.5 year enrolment plus 1 year follow-up): follow-up visits at 4-6 weeks and 1 year post-operatively.
Study Device:	X-PSI Knee System
Scores:	VAS (pain), EQ-5D, Oxford Knee Score
Documentation:	Electronic Data Capture, Oracle

2 Statistical Considerations/ Evaluation

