2.2 Data Analysis

Data will be analyzed using SAS 9.4 or higher. The Type I error rate for the primary study analysis will be 0.05. Comparisons for secondary, exploratory, and safety analyses will be two-sided comparisons using $\alpha = 0.05$, with no adjustment for multiple comparisons.

Primary Analysis: The primary analysis will be conducted on the as-treated data set. In the as-treated-analysis for the primary endpoint, missing data will be treated as described in Section 1.1.

The primary endpoint is to show achievement of mechanical leg alignment in HKA frontal plane (± 3 degrees) with X-PSI Knee System is as accurate as with standard instrumentation at 4-6 weeks post operation. The X-PSI Knee System cohort will be compared with current literature (70% of cases within ± 3 degrees).

To determine the upper and lower limits with 95% confidence that 70% of the X-PSI patients' HKA frontal plane measurements are contained, a 70% tolerance interval will be constructed based on the mean and standard deviation of the HKA frontal plane measurements from patients in the study. A tolerance interval is defined as "a statistical interval within which, with some confidence level, a specified proportion of a sampled population falls". In this study, we will claim with 95% confidence that 70% of the X-PSI patients fall within a computed tolerance interval. This method allows us to state an upper and lower limit in which we can claim 70% of the alignments will fall within with a given confidence (95%).

The upper and lower tolerance limits are defined as

$$Y_L = \bar{Y} - K \cdot s; \quad Y_U = \bar{Y} + K \cdot s;$$

where Y_L and Y_U are the lower and upper tolerance limits respectively, \bar{Y} is the sample mean, s is the sample standard deviation and k is defined as

$$K = \sqrt{\frac{v\left(1 + \frac{1}{N}\right)z_{(1-p)/2}^2}{X_{1-y,v}^2}}$$

where p is the percentage (proportion) of the population we want to claim within the interval, $X_{1-y,v}^2$ is the critical value of the chi-square distribution with degrees of freedom v that is exceeded with probability y , and $z_{(1-p)/2}$ is the critical value of the normal distribution associated with cumulative probability $(1-p)/2$.

For this study, $p = 0.7$ (70%), and $y = 0.95$ (95%). The study will be considered a success if both the upper and lower tolerance limits are within $+\/- 3$ degrees.

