2.3 Sample Size

Based on preliminary U.S. IDE data, we estimate the standard deviation to be 1.62. Based on the above formula for calculating tolerance intervals, a sample size of 60 will allow us to claim that 70% of the alignments fall within $+\/- 2$ degrees. The sample size formula plans for $+\/- 2$ degrees to account for the initial IDE data showing the average offset is about -1 degrees and our goal is to show that 70% or more are within $+\/- 3$ degrees. To account for loss to follow up and patient dropouts, enrolling 70 patients includes a 10% loss to follow-up to ensure there are 60 patients at the end of the study.

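### The hypothesis and primary endpoint claim equal accuracy with conventional instrumentation, but the single-arm tolerance rule can support only the goal of at least 70% within ±3°.

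*Combined protocol and SAP*

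**What the plan says.** The Synopsis hypothesis is that X-PSI "achieves the same accuracy with respect to mechanical alignment as with conventional instrumentation". The primary endpoint in the Synopsis, repeated in section 2.2, is that alignment in the HKA frontal plane (±3°) "is as accurate as with standard instrumentation at 4-6 weeks post operation". The Synopsis adds that the cohort will be "compared with current literature (70% of cases within ± 3 degrees). No control group will be studied".

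Section 2.2 sets one primary criterion. A 70%/95% normal tolerance interval is built from the mean and SD of the study patients, and "The study will be considered a success if both the upper and lower tolerance limits are within" ±3°. It also states: "The Type I error rate for the primary study analysis will be 0.05". It does not say whether that rate is one- or two-sided.

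Section 2.3 gives the planning basis: "we estimate the standard deviation to be 1.62" degrees, and "a sample size of 60 will allow us to claim that 70% of the alignments fall within" ±2°. The ±2° is used because of "the initial IDE data showing the average offset is about -1 degrees and our goal is to show that 70% or more are within" ±3°.

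**The concern.** Two different primary claims stand side by side. The hypothesis and endpoint speak of equality with another technique. The success rule and the stated goal in section 2.3 concern a minimum share of X-PSI cases inside ±3°. The rule uses no conventional-instrument data, has no equivalence or non-inferiority margin, and treats the 70% as known without error. Its result would be the same whatever conventional instruments achieve.

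The wording matters whichever way the study ends. A success could be reported under a hypothesis that was not tested. A miss could be taken as evidence against X-PSI, although the rule is stricter than the goal when the mean is off zero and can fail often when the goal is comfortably met. The plan defines success only and does not say how a miss should be read.

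**Working it through.** **Inputs.** Content p = 0.70, confidence 0.95 and the ±3° limits are from section 2.2. SD 1.62°, mean offset about -1°, N = 60 and 70 enrolled with 10% loss are from section 2.3. I assume normal data and read HKA as a deviation whose ideal value is 0°.

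**1. The plan's own figure.** K = √[v(1 + 1/N)z² / χ²], with v = 59, z = 1.0364 and lower 5% chi-square quantile 42.34.
- K(60) = √[59 × (61/60) × 1.0364² / 42.34] = 1.2336, and 1.2336 × 1.62 = 1.998°.
- N = 59 gives 2.002°, so 60 is the smallest N that meets ±2°. The figure reproduces.
- Enrolling 70 with 10% loss leaves 63, which covers it.

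**2. What success supports.** The rule amounts to |mean| + K·s ≤ 3. I set the true share within ±3° to exactly 70% and integrated over the normal distribution of the mean and the chi-square distribution of s² at N = 60.
- Mean 0° (SD 2.895°): the rule passes about 1.0% of the time.
- Mean -1° (SD 2.709°): it passes about 0.16% of the time.

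Both are below the stated 0.05, so success is sound evidence for at least 70%. Nothing in the rule refers to conventional instrumentation or sets an upper bound, so it does not address sameness.

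**3. How much stricter than the goal the rule is.** In large samples K tends to 1.0364, so the rule needs SD ≤ (3 - |mean|)/1.0364.

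| Mean | Largest SD | Share within ±3° |
|---|---|---|
| 0° | 2.895° | 70.0% |
| -0.5° | 2.412° | 77.7% |
| -1° | 1.930° | 83.1% |

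The reason is that each limit in effect allows 15% beyond it. With an off-centre mean the near tail uses its 15% while the far tail is almost empty. At N = 60, an observed mean of -1° needs an observed SD of at most 2/1.2336 = 1.621°, a fitted share of 88.5%.

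**4. Chance of success at the planning values.** The true share is Φ(4/1.62) - Φ(-2/1.62) = 0.9932 - 0.1085 = 0.885. The expected lower limit is about -1 - 1.998 = -2.998°, right on the boundary.
- At mean -1°, the success probability is 0.516 (N = 60), 0.530 (N = 63) and 0.560 (N = 70).
- At N = 60 and SD 1.62°, it is about 0.83 at mean -0.75° and 0.19 at mean -1.25°.

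**5. An exact binomial rule for the same goal, N = 60.** Here the one-sided 95% lower bound for the proportion must exceed 70%.
- 49 of 60 gives a bound of 71.5%; 48 of 60 gives 69.6%. The threshold is therefore 49, with size 2.9% and power about 96% at the planning values.
- A threshold of 52 of 60 has size 0.22%, close to the tolerance rule's 0.16% at mean -1°, and power about 75%.
- The gain is 96 - 52 = 44 points. Of these, 96 - 75 = 21, about half, come simply from using more of the 5% error rate.

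**The case against.** The strongest reply is that the plan hides nothing. The study is titled non-controlled, the endpoint itself names the literature comparator and rules out a control group, section 2.2 says what will be claimed with 95% confidence, and section 2.3 states the goal as 70% or more. On that reading, the as-accurate-as wording is shorthand for meeting the benchmark. This stands as far as disclosure goes: a reader might infer a concealed design flaw, and the documents do not support that. But disclosing a fixed benchmark does not turn the test into one of sameness. Even if 70% were the true conventional rate, success would be a one-sided result above it, which is not equality.

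Other tempting readings also go too far.
- *That success shows nothing beyond 70%.* The rule is stricter than 70% when the mean is off zero, and it also yields the upper and lower limits that section 2.2 wants.
- *That the plan ignores the offset.* Section 2.3 tightens ±3° to ±2° because of it. What is missing is the implied share and the chance of success.
- *That the plan would read a miss as inferiority.* It says no such thing; it is silent.
- *That 52% against 96% shows the rule must be replaced.* The two rules run at very different true error rates, and the 52% depends heavily on a mean given only as about -1°.

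**Conclusion.** The mismatch is real and should be corrected, but it does not invalidate the study. The sample size arithmetic reproduces and the success rule is a valid, conservative test of the goal in section 2.3. What the test cannot carry is the equality claim in the hypothesis and primary endpoint.

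Two consequences of the rule also need stating. At an offset of -1° it demands about 83% within ±3° in large samples, not 70%. With 60 patients at the planning values it succeeds in about 52% of studies although 88.5% of cases truly lie within ±3°; so a miss, expected in about 48%, would say little about X-PSI against conventional instrumentation.

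These figures rest on normal data and the plan's SD of 1.62°. The success probability is sensitive to the mean. The conclusion about the wording depends on none of these numbers.

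**What to change.** **Needed.**
1. In the Synopsis and section 2.2, restate the hypothesis and primary endpoint as a performance goal: at least 70% of X-PSI cases lie within ±3°, against a fixed literature figure whose source is named. Remove the wording that claims equal accuracy with conventional or standard instrumentation.
2. State that missing the criterion does not show lower accuracy than conventional instrumentation.
3. In sections 2.2 and 2.3, state that the rule is stricter than the goal when the mean is not 0 (about 83% at -1° in large samples). Give its pass rates at a true share of 70% and N = 60 (about 1.0% at mean 0°, 0.16% at mean -1°) beside the stated 0.05. Give the success probability at the planning values, with its range over plausible means.

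This is wording and disclosure only: no extra patients and no change of analysis. The price is a narrower claim and a less favourable stated chance of success. Keeping the rule and raising that chance to 80% at the planning values would take about 154 analysed cases.

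**Optional, and only if fixed before any data are analysed.** Define success as an exact one-sided 95% lower bound for the proportion within ±3° above 70% (at least 49 of 60). It needs no normality assumption and has power of about 96% at the planning values. However, about half of the gain comes from spending more of the 5% error rate, it dichotomises a continuous measure, and it gives up the tolerance limits as the basis for success. This is the sponsor's choice, not a required correction.

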Secondary Analysis: Analyses for secondary endpoints will be conducted on the as-treated data set, and will only use those cases with complete data for the endpoint being analysed.

Continuous data (e.g. age, BMI, VAS pain) will be reported using mean, standard deviation, median, and range. Categorical data (e.g. gender) will be reported using frequency and percentage.

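### Does calling three procedure times in an uncontrolled cohort cost-effectiveness require a change to the secondary endpoint?

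*Combined protocol and SAP*

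**What the plan says.** The Endpoints row of the Synopsis defines the only endpoint labelled secondary as "Cost-effectiveness as assessed by OR set-up time, surgery time and post-processing time". The primary-endpoint text in the same row states "No control group will be studied", and the Study Design row confirms that the whole study is non-controlled. The Number of Subjects row reads "Data will be collected from 70 TKA cases implanted by use of the X-PSI Knee System in up to 5 study centers", so every recorded time will come from an X-PSI case. The Scores row lists "VAS (pain), EQ-5D, Oxford Knee Score" without tying any of them to cost.

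Two parts of Section 2.2 (Data Analysis) bear on how the times are analysed:

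- The opening paragraph sets a general rule: "Comparisons for secondary, exploratory, and safety analyses will be two-sided comparisons using" an alpha of 0.05, unadjusted for multiplicity.
- The Secondary Analysis paragraph sets the data set and the method: "Analyses for secondary endpoints will be conducted on the as-treated data set, and will only use those cases with complete data for the endpoint" in question, and "Continuous data (e.g. age, BMI, VAS pain) will be reported using mean, standard deviation, median, and range".

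**The concern.** Cost-effectiveness normally means a difference in cost set against a difference in effect, relative to an alternative. Here there is no alternative arm, no stated cost and no effect measure joined to the times. A mean surgery time from X-PSI cases alone cannot say whether the system saves or loses time, and still less whether it is worth its price. If the label were carried into the report as a conclusion, readers would be given an economic finding that the design cannot produce.

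The alpha rule in Section 2.2 adds some unease. It allows for secondary comparisons but names nothing to compare the times with. If a reference time were chosen after the data were seen, that choice could decide the direction of the result. What post-processing covers, and when each time starts and stops, is also not stated in the Synopsis or Section 2.

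**Working it through.** **The plan's own figure.** The only calculated design figure is the 60 evaluable patients in Section 2.3, and it concerns alignment. With the tolerance factor of Section 2.2 (p = 0.70, confidence 0.95, v = N − 1) and the stated SD of 1.62:

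- N = 60: K = 1.2336, half-width 1.2336 × 1.62 = 1.998 degrees, inside the planned ±2.
- N = 59: K = 1.2357, half-width 1.2357 × 1.62 = 2.002 degrees, just outside.

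So 60 is reproduced. It uses no time or cost input, and nothing about the secondary endpoint feeds into it. No design figure is given for the times, so the rest of the check compares the text.

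**What an economic conclusion would need, against what the text gives.**

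| Input | Found in the Synopsis or Section 2? |
|---|---|
| Comparator times | No. The only external benchmark is for alignment (70% of cases within ±3 degrees). |
| Unit costs | No. |
| Effect measure joined to cost | None stated. EQ-5D and Oxford Knee Score are listed only as scores. |

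The third row matters less than the first two. The Synopsis hypothesis is that X-PSI matches conventional instrumentation for accuracy. If effect is taken as equal, an economic comparison can rest on resource use alone, with time as a proxy. Equal accuracy is a hypothesis here, not an established fact, so this narrows the gap to comparator and costs without closing it. Either way, the times support description only.

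**What the plan does with the times.**

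1. Synopsis, Endpoints: one use of the term, with its meaning given in the same sentence as three durations.
2. Section 2.2, alpha rule: covers any secondary, exploratory or safety comparison that is made. It names no contrast for the times and does not require one.
3. Section 2.2, Secondary Analysis: as-treated set, complete cases for the endpoint, then mean, SD, median and range for continuous data.
4. Section 2.4 (Study Report): sets the timing of the primary analysis and refers back to the methods. It adds no economic analysis.

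Planned cost-effectiveness ratios, thresholds, tests or claims: none.

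**What renaming would alter.** Suppose the endpoint were called time measures with X-PSI. The same three durations would be collected from the same cases and summarised by the same four statistics on the same data set. The success rule depends only on the tolerance limits for HKA, and the sample size only on the SD and offset of HKA. The number of planned results that change is zero.

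A confidence interval for each mean time would not help either. It would show how well the X-PSI mean is known, not how that mean compares with anything else.

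**The case for a change.** The best case for a change is that it costs almost nothing. The phrase in the Synopsis makes the times the whole definition of cost-effectiveness rather than one input to a model described elsewhere. A descriptive table printed under that heading still invites a conclusion. The primary endpoint has its literature benchmark fixed in advance and the times have none, so a later comparison would be open to a convenient choice of reference. Defining the three times and disclaiming an economic conclusion would take a few lines.

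Part of this stands. The label is looser than it should be, and any later comparative or economic statement would need reference times with a source and unit costs, chosen before the data were seen. But that condition attaches to a claim the plan does not make. The general alpha rule does not create the claim, because a two-sided level has no use without a contrast.

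The request for definitions is reasonable only if they are absent from the full plan, which the synopsis and statistics text cannot settle. Section 2.2 cites a Section 1.1 and Section 2.4 cites a Section 1.2, where the matching text is numbered 2.1 and 2.2. This hints, without proving it, that the statistics text was taken from a document with different numbering. The suspicion that the surgeon's review of the preoperative plan goes uncounted is conjecture: that review is mentioned only in connection with the accuracy comparison, and nothing shows that its time is left out.

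**Conclusion.** The observation is correct but calls for no change. Three times from one uncontrolled cohort cannot support a cost-effectiveness conclusion in either direction. The plan draws no such conclusion and already prescribes the descriptive summaries the data can bear. A new name would change no analysis set, statistic, success rule or sample size, so the gain in results is zero. An analyst following Section 2.2 would tabulate the times as times, and the missing start and stop definitions are detail that a study team ordinarily fills in its data-collection instructions.

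This rests on two assumptions: that the report keeps to the summaries in Section 2.2, and that no economic or comparative claim about the times is added later. If one were added, it would have to be judged as a new analysis with its own comparator and costs.

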2.1 Handling of Missing and Incomplete Data

Data will be considered "missing" for the primary endpoint if this outcome cannot be determined or is unavailable for a subject. Every effort will be made to collect the data necessary to evaluate the primary endpoint. Patients who have been lost to follow-up and do not have mechanical leg alignment in HKA frontal plane data at 4-6 weeks will not be included in the primary study analysis.

Sensitivity analyses will be performed to assess the impact of missing data on the primary study analysis. These analyses may include a best-case and worst-case imputation as well as a tipping point analysis.

2.2 Data Analysis

Data will be analyzed using SAS 9.4 or higher. The Type I error rate for the primary study analysis will be 0.05. Comparisons for secondary, exploratory, and safety analyses will be two-sided comparisons using $\alpha = 0.05$, with no adjustment for multiple comparisons.

Primary Analysis: The primary analysis will be conducted on the as-treated data set. In the as-treated-analysis for the primary endpoint, missing data will be treated as described in Section 1.1.

The primary endpoint is to show achievement of mechanical leg alignment in HKA frontal plane (± 3 degrees) with X-PSI Knee System is as accurate as with standard instrumentation at 4-6 weeks post operation. The X-PSI Knee System cohort will be compared with current literature (70% of cases within ± 3 degrees).

To determine the upper and lower limits with 95% confidence that 70% of the X-PSI patients' HKA frontal plane measurements are contained, a 70% tolerance interval will be constructed based on the mean and standard deviation of the HKA frontal plane measurements from patients in the study. A tolerance interval is defined as "a statistical interval within which, with some confidence level, a specified proportion of a sampled population falls". In this study, we will claim with 95% confidence that 70% of the X-PSI patients fall within a computed tolerance interval. This method allows us to state an upper and lower limit in which we can claim 70% of the alignments will fall within with a given confidence (95%).

The upper and lower tolerance limits are defined as

$$Y_L = \bar{Y} - K \cdot s; \quad Y_U = \bar{Y} + K \cdot s;$$

where Y_L and Y_U are the lower and upper tolerance limits respectively, \bar{Y} is the sample mean, s is the sample standard deviation and k is defined as

$$K = \sqrt{\frac{v\left(1 + \frac{1}{N}\right)z_{(1-p)/2}^2}{X_{1-y,v}^2}}$$

where p is the percentage (proportion) of the population we want to claim within the interval, $X_{1-y,v}^2$ is the critical value of the chi-square distribution with degrees of freedom v that is exceeded with probability y , and $z_{(1-p)/2}$ is the critical value of the normal distribution associated with cumulative probability $(1-p)/2$.

For this study, $p = 0.7$ (70%), and $y = 0.95$ (95%). The study will be considered a success if both the upper and lower tolerance limits are within $+\/- 3$ degrees.

Secondary Analysis: Analyses for secondary endpoints will be conducted on the as-treated data set, and will only use those cases with complete data for the endpoint being analysed.

Continuous data (e.g. age, BMI, VAS pain) will be reported using mean, standard deviation, median, and range. Categorical data (e.g. gender) will be reported using frequency and percentage.

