2.4 Study Report

The primary analysis will be performed after all patients reach the 4-6 weeks follow up time point. Data will be analysed using the methods described in Section 1.2.

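### The tolerance-interval success rule is stricter than the stated goal of 70% within ±3°, and at the plan's own values it succeeds only about half the time

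*Combined protocol and SAP*

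**What the plan says.** The Synopsis and section 2.2 set the benchmark as a proportion taken from the literature: 70% of cases within ±3° in the HKA frontal plane. Section 2.3 repeats it as the aim: "our goal is to show that 70% or more are within" ±3°.

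The decision rule in section 2.2 uses a normal tolerance interval, mean ± K·s, with content 70% and confidence 95%: "The study will be considered a success if both the upper and lower tolerance limits are within" ±3°. The same section adds "The Type I error rate for the primary study analysis will be 0.05" without giving a side, whereas for the other analyses it says "Comparisons for secondary, exploratory, and safety analyses will be two-sided comparisons".

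Section 2.3 takes SD 1.62° from earlier data and states that "a sample size of 60 will allow us to claim that 70% of the alignments fall within" ±2°. The narrower figure of 2° is used "to account for the initial IDE data showing the average offset is about -1 degrees". On attrition it says "enrolling 70 patients includes a 10% loss to follow-up", to leave 60. Neither section states a power or a probability of success.

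**The concern.** The goal is about the share of cases inside a fixed band centred on zero. The rule is about an interval centred on the sample mean. The two coincide only when the mean is zero. If the mean is shifted, the near limit reaches the edge of the band first, and cases between the far tolerance limit and the far edge earn no credit.

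The sizing adds a second problem. It sets the expected half-width at 2° and the expected offset at 1°, which together use up the whole 3°. Nothing is left for sampling error in the mean or the SD. A design whose expected statistic sits on its own cut-off passes about half the time, so the statement that 60 patients allow the claim promises more than the design delivers. At stake is a negative primary result for a device that meets the stated goal.

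**Working it through.** **Inputs.** From section 2.2: p = 0.70, y = 0.95, band ±3°, type I error 0.05. From section 2.3: SD 1.62°, mean about -1°, N = 60, 70 enrolled, 10% loss (70 × 0.9 = 63). Assumptions: normal data; v = N - 1; -0.5° to -1.5° as a reading of "about -1", since the plan gives no spread for it.

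**1. Reproducing N = 60.** K = √[v(1 + 1/N)·z²/χ²], with z = 1.0364 and χ² the lower 5% point on v degrees of freedom. At N = 60: K = √(59 × 61/60 × 1.0742 / 42.339) = 1.2336, and K × 1.62 = 1.9985°. At N = 59 the half-width is 2.002°. So 60 is exactly the smallest N with a half-width of at most 2°, and the plan's figure is right.

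**2. The planned limits.** -1 - 1.9985 = -2.998° and -1 + 1.9985 = +0.998°. The lower limit is on the boundary; the upper is 2° inside it.

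**3. Probability of success.** P(-3 + K·s < mean < 3 - K·s), integrated over s² ~ SD²·χ²_v/v with mean ~ N(μ, SD²/N). SD 1.62°, N = 60, beside an exact binomial test of 70% on the same 60 cases (pass at 49 or more):

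| True mean | True share within ±3° | Tolerance rule | ≥49/60 |
|---|---|---|---|
| -0.5° | 92.3% | 0.97 | 0.998 |
| -0.8° | 90.3% | 0.78 | 0.99 |
| -1.0° | 88.5% | 0.52 | 0.96 |
| -1.2° | 86.2% | 0.25 | 0.88 |
| -1.4° | 83.5% | 0.08 | 0.72 |
| -1.5° | 82.0% | 0.04 | 0.61 |

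The tolerance rule reaches 80% only if the offset is no larger than about 0.78°. With 63 evaluable cases it gives 0.53 at -1°. At -1° and N = 60 it gives 0.73 for SD 1.5° and 0.38 for SD 1.7°.

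**4. How strict the rule is.** In an infinite sample it passes if |μ| + 1.0364·SD ≤ 3. At the largest SD that passes, the share within ±3° is 70% at μ = 0, 77.7% at -0.5°, 83.1% at -1° and 84.9% at -1.5°. At SD 1.62° no sample size gives an even chance once the offset exceeds 3 - 1.0364 × 1.62 = 1.32°.

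**5. Validity.** With the true share at exactly 70% and N = 60, the rule passes with probability 0.0104 at mean 0, 0.0067 at -0.5°, 0.0016 at -1° and 0.0002 at -1.5°, all below 0.05.

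**6. Same data, two rules.** In simulation (400,000 trials per setting, N = 60), ≥49/60 passes while the tolerance rule fails in 3% of trials at -0.5°, 21% at -0.8°, 44% at -1°, 63% at -1.2° and 57% at -1.5°. The reverse at -1° occurs in under 0.01%. With ≥50/60 the figure at -1° is 40%. Among trials at -1° that fail the tolerance rule, the median count is 52/60, with a one-sided 95% lower bound of 77.2%. At exactly 49/60 that bound is 71.5%, so the weakest of these datasets exceed 70% only narrowly.

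**7. A bound that keeps the normal model.** A one-sided 95% lower bound on the proportion within ±3°, by generalised pivotal quantities at N = 60, gives power 0.998 at -1°, 0.99 at -1.2° and 0.83 at -1.5°, with simulated type I error of 0.03 to 0.04.

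**The case against.** The strongest reply is that the strictness may be deliberate. Section 2.2 sets out to give two limits and requires both to lie inside the band, and section 2.3 knowingly reserves 1° for the offset. In an accuracy study a criterion that penalises systematic offset is defensible, and the rule is pre-specified and conservative. A pure proportion gives up that protection: at a true mean of -1.5°, ≥49/60 passes 61% of the time against 4% now. Part of the 44% discordance also reflects the two rules' different attained type I errors. And 0.52 takes "about -1" as exactly -1.0° and the SD as exactly 1.62°.

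Much of this stands as a reason to make any rule change conditional. It does not remove the point. The Synopsis and sections 2.2 and 2.3 all word the target as a proportion, and nowhere does the plan say that more than 70% is required. The 1° reserve covers the expected offset but not sampling error. The sensitivity to the offset is itself a reason to show the probability of success over a range.

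Keeping the strict bar with conventional power is possible but not cheap: at -1° and SD 1.62° the unchanged rule needs about 154 evaluable cases for 80% and 226 for 90%.

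**Conclusion.** The concern holds and should be fixed. The primary rule is valid but does not match the stated goal when the mean is off zero, and the plan expects it to be. At the planning values the chance of success is about 52% with 60 cases and 53% with 63, although 88.5% of cases would lie within ±3°. No power is stated. The error runs one way: the type I error is at most about 1%, so the cost is false failure.

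These figures rest on normal data and the plan's SD. The 52% uses only the plan's own values; the spread from 0.97 to 0.04 rests on the assumed range of -0.5° to -1.5°.

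**What to change.** **1. In every case.** State in section 2.3 the rule's probability of success over a range of offsets (0.97 at -0.5°, 0.52 at -1°, 0.04 at -1.5° for N = 60; 0.53 at -1° for N = 63). State in section 2.2 whether a bar stricter than 70% is intended.

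**2. If it is not intended, and only before the sponsor or any site has seen a postoperative alignment result.** Amend section 2.2 to: *Success if the exact (Clopper-Pearson) one-sided 95% lower confidence bound for the proportion of cases within ±3° exceeds 70%.*
- The cut-offs are ≥49/60, ≥51/63 or ≥56/70, with attained alpha 0.029, 0.035 and 0.041.
- State the side. If one-sided 0.025 is meant, the cut-offs are ≥50/60, ≥52/63 or ≥57/70; power for ≥50/60 is 0.92 at -1°, 0.80 at -1.2° and 0.47 at -1.5°.
- The normal-model lower bound on the same proportion is an acceptable alternative. It has more power and avoids dichotomising, but relies on normality as the current rule does.
- Keep the tolerance interval, and the mean offset with its confidence interval, as supportive results.
- Restate section 2.3 with the new rule's power over the same offsets.

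**3. If alignment results have been seen, or the offset-penalising bar is intended.** Keep the rule and make only change 1.

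**Cost.** Text in sections 2.2 and 2.3; no extra patients or images. Timing matters because section 2.4 says "The primary analysis will be performed after all patients reach the 4-6 weeks follow up time point", and easing a success criterion in an uncontrolled study once results are known would damage its credibility. The new rule does not separately penalise an offset, so the mean offset must be reported beside it. At zero offset the binomial gains little: at a true 85% it gives 0.82 against 0.79 for the tolerance rule, and 0.72 against 0.79 at one-sided 0.025. The normal-model bound gives 0.96 and 0.90 there.
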